Study Protocol

A randomised controlled trial:

Delivery of local anaesthesia through adductor canal

catheter after total knee arthroplasty

(DETACH-TKA)

[name] - Regional Anaesthesia Fellow

[name] – Specialist Anaesthetist

Protocol Synopsis

Study Title:
	
A randomised controlled trial: Delivery of local anaesthesia through Adductor Canal catheter after Total Knee Arthroplasty (DETACH-TKA)

Objective(s):
	
 • To find a superior technique (between two methods) of delivering local anaesthesia through an adductor canal catheter after total knee arthroplasty (TKA). • To improve perioperative care pathways for patients having TKA, locally and beyond.

Study Design:
	
 • Prospective, randomised controlled trial comparing continuous infusion of local anaesthesia (5mls/hr of 0.2% Ropivacaine) with programmed intermittent bolus (10mls of 0.2% Ropivacaine bolus every 2 hours) down an adductor canal catheter after TKA. • The local anaesthesia will be administered for 48 hours after commencement in the postoperative care unit (PACU). • Aside from the difference in local anaesthesia delivery down the adductor canal catheter, both groups will receive the same care. 
Primary outcomes will be total opioid consumption over 48 hours (conversion to total oral morphine equivalents). Secondary outcomes will include Quality of Recovery (QoR-15) questionnaire, time to first assisted mobilisation, number of doses of antiemetic, hospital length of stay, timed up-and-go tests, and side effects at specified time intervals (24, 48, 72 hours after commencement of study infusion).

Subject population and duration:
	
Patients undergoing a primary total knee arthroplasty at Counties-Manukau District Health Board facilities. We expect the study to be completed in 6-9 months.

Contents

1. Project overview
 - 1.1 Principle purpose
 - 1.2 Background
 - 1.3 Patient population
 - 1.4 Number of patients
2. Research methods
 - 2.1 Study Design
 - 2.2 Inclusion and Exclusion Criteria
 - 2.3 Suggested Perioperative Pro Forma
 - 2.4 Placement of the Adductor Canal Catheter
 - 2.5 Trial Assessments
 - 2.6 Benefit to participants
- 3 Statistical considerations
- 4 Data collection and retention
- 5 Ethics and Responsibility
- 6 Conclusions
- 7 Bibliography

1. Project Overview

1.1 Principle Purpose

Patients may experience significant pain following Total Knee Arthroplasty (TKA) which can delay rehabilitation and result in poorer short and long term outcomes. The use of an adductor canal catheter for two to three days after surgery can significantly reduce opiate analgesic consumption, improve patient satisfaction, and increase the ability to participate in rehabilitation.

The primary aim of this project is to compare and determine the superior technique for the delivery of local anaesthesia down the adductor canal catheter following TKA. This study is designed so that participants are randomized into two groups in a 1:1 fashion; one group will receive a continuous infusion of local anaesthetic (5mls/hr of 0.2% Ropivacaine), and the second group will receive a programmed intermittent bolus (PIB) of 10mls of 0.2% Ropivacaine every two hours. This is a positive-control study with no placebo group. The local anaesthetic will be delivered for 48 hours after commencement in the postoperative care unit.

There is evidence that the use of PIB leads to improved postoperative analgesia as seen by reductions in opiate consumption without side effects. Besides from the difference in local anaesthesia delivery down the adductor canal catheter, both groups will receive the same care as outlined in research methodology.

This study may identify the superior method of administration of local anaesthetic so that future patients undergoing a TKA can have a better experience, and speedier recovery.

1.2 Background

Total knee arthroplasty (TKA) is offered to patients with significant disorders of the knee arising from ageing, degenerative disease or after trauma. With the ageing population, this procedure will become more frequent and consume increasing amounts of health care resources (1). Current guidelines for TKA patients place an emphasis on early mobilisation and discharge to back to the community for home-based rehabilitation (2).

Despite the potential for considerable functional improvement after surgery, TKA is a painful procedure (4). The perioperative analgesic management is one area in which the anaesthetist can influence patient satisfaction and early joint function. To facilitate early mobilisation and rapid discharge, there has been a shift away from traditional techniques that produce systemic side effects or motor weakness - both which hamper post-operative rehabilitation efforts (2,5).

At Counties Manukau Health, the use of high-volume infiltration of low concentration local anaesthesia (LIA) has become the cornerstone of pain management following TKA. This technique is supplemented with multimodal oral analgesia and/or peripheral nerve catheters. A recent study conducted at Counties Manukau confirmed the relative safety of LIA with no observations of toxicity after recording peak local anaesthesia levels between six and twenty-four hours after surgery indicating that there is capacity for additional local anaesthetic use in the perioperative period (6).

As the levels of local anaesthetic begin to fall, evidence from randomized controlled trials and metaanalyses suggest analgesic efficacy of LIA begins to wane (7). To prolong the duration of effective non-opioid analgesia, the anaesthetist can place a

peripheral nerve catheter under ultrasound guidance near the nerves supplying sensation to the operative knee. One such example is the adductor canal catheter (ACC) which provides ongoing pain relief by using local anaesthesia to dampen pain signals generated from the operative site (8,9). The ACC prolongs analgesia without significant motor blockade; patients are less reliant on opioid analgesia and are able to participate in rehabilitation. Evidence from randomised controlled trials suggests that the ACC is a safe intervention which is complementary, and may enhance, the effect of LIA (10).

Post-operative use of an ACC after TKA was first trialled at Counties-Manukau Health in 2015 and it has increasingly been utilised by anaesthetists to achieve the goals as outlined above. In 2018, the Department of Anaesthesia and Pain Medicine enrolled patients in an international trial to determine the most effective site of catheter insertion, the results of which are yet to be published.

There is considerable debate as to what constitutes the most effective method of local anaesthetic administration through peripheral nerve catheters (11). Two potential options include the continuous administration of a fixed amount of local anaesthetic each hour or the use of a programmed intermittent bolus (PIB) whereby a bolus of local anaesthetic is provided every one to two hours through the catheter. PIB may result in greater spread of local anaesthetic which may lead to improved analgesic outcomes (12). Our department has recently completed a meta-analysis which concluded that PIB may be more efficacious, especially for lower limb catheters, than continuous local anaesthetic administration. The benefits seen included a reduction in total local anaesthetic and opioid consumption with no deleterious effect on patient satisfaction or side effects (article submitted for publication).

1.3 Patient Population

This is a study of two techniques of local anaesthesia delivery down an adductor canal catheter in patients who will have an elective unilateral primary total knee arthroplasty through Middlemore hospital and Manukau Super Clinic.

The cohort of patients undergoing this procedure tend to be older, with the majority between 50 to 80 years of age with no discrimination by either sex or ethnicity.

Currently, Counties-Manukau Health performs approximately 450 TKAs per annum at Middlemore Hospital and Manukau Surgical Centre.

With the ageing population, we project that the number of patients undergoing TKA will continue to grow in the years to come. Optimisation of our local care pathways is vital to ensure patients receive cost-effect evidence-based best practice. With this study, we aim to improve on our care pathways to aide future patients undergoing a TKA in our institution and beyond.

1.4 Number of Patients

The study size will depend on the power calculation. This information is yet to be collected. Similar trials testing for differences in effect between continuous and intermittent bolus techniques have enrolled between 40 to 60 patients. Once the clinically significant treatment effect has been determined, we will calculate the sample size using standard techniques with $\alpha = 0.05$ and $\beta = 0.2$

2. Research Methods

2.1 Study Design

This is a prospective randomized controlled trial for patients undergoing an elective, unilateral primary total knee arthroplasty. We aim to randomly allocate participants to one of two groups in a 1:1 fashion. The first group will receive a continuous infusion of local anaesthetic whereas the second group will receive a programmed intermittent bolus. Besides from this difference, the participants will all receive routine care after their TKA; this is a positive-control study in which there will be no placebo group. Both the participants and the research nurse assessing patient outcomes will not be aware of group allocations.

2.2 Inclusion Criteria

We aim to enrol patients undergoing primary TKA in our institution prior to the day of surgery in the preadmission clinic or on the day of surgery at the time of surgical and anaesthetic consent. Adequate time for patient questions and a plain language explanation sheet will be provided to aid patient consent. The study will be completed at Middlemore Hospital and Manukau Surgical Centre. Consultation with the Maori and Pacific representatives will be sought as per current HDEC standards.

2.2 Exclusion criteria

- Refusal or inability to consent.
- Analgesic technique involving epidural or peripheral nerve blockade (single shot or continuous techniques)
- Nerve catheter placed outside accepted range (distal to femoral triangle down to the adductor canal)
- Allergies to medication used in the study or its constituents
- Significant kidney and liver dysfunction (CrCl < 30mls/min, AST/ALT >2x upper limit of normal)

- Surgical procedure performed outside of Counties Manukau Health facilities.
- Failure to site adductor canal catheter in the appropriate location.
- Patients on >30mg/day of oral morphine equivalent for any reason.
- Patients outside the specified age range of 18-80 years.
- Patients at extremes of weight e.g.<50kg or >150kg
- If surgical team do not wish to take part or give individually tailored treatment that violate study protocol.

The Anaesthetic and Surgical management of patients enrolled in this study is largely at the discretion of the treating specialists after discussion with the patient. An anaesthetic pro forma is suggested below – data surrounding deviation from this pro forma will be collected and included in the final analysis.

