2.4 Placement of the Adductor Canal Catheter

At the end of surgery after sterile surgical dressing have been applied, an ultrasound guided adductor canal catheter will be placed on the operative limb using an aseptic technique. A multiorifice catheter (e.g. Contiplex or Contiplex C *B.Braun AG, Melsungun, Germany*) should be placed either within the distal femoral triangle or within the adductor canal deep to the Sartorius muscle. At least 2cm catheter should be left beyond the end of the needle. The catheter can be secured with both tissue glue and/or a catheter anchoring device prior to the administration of a sterile dressing.

No local anaesthetic will be administered down the catheter until the attachment of the prescribed infusion in the post-anaesthesia care unit (PACU). Randomisation will have taken place using opaque envelopes. Both the participants and the research nurses will not be aware which treatment a particular patient is receiving whereas the PACU nurses involved in the programming of the infusion pump and attaching the infusion to the patient will not be blinded. Participants will be randomised to receive either:

1. Continuous infusion group – 5 mls/hr of ropivacaine 0.2% for 48 hours
2. Programmed intermittent bolus group – 10mls ropivacaine 0.2% every two hours for 48 hours.

The time of infusion commencement will be noted down and the trial will run for 48 hours from this point. During this trial period, the assessments will take place at specified time points; 24 hours, 48 hours and 72 hours after the commencement of the infusion.

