2.5 Trial Assessments

Primary outcome:

Total opioid consumption over 48 hours. This will be converted to oral morphine equivalents as per the methods prescribed by the Faculty of Pain Medicine of the Australian and New Zealand College of Anaesthetists.

(<http://fpm.anzca.edu.au/documents/opioid-dose-equivalence.pdf>)

Secondary outcomes:

- Quality of Recovery (QoR-15) scores collected 24 and 48 hours after commencement of the study infusion.
- Time to first assisted mobilisation measured in minutes after discharge from PACU.
- Passive range-of-movement on day 1 and day 2, 24 and 48 hours after commencing the study infusion.
- Number of doses of antiemetic required over the 48-hour study period.
- Hospital length of stay measured in days.
- Side effects including nausea and vomiting, pruritis and sedation (Pasero opioid-induced sedation scale) collected daily.
- “Timed up and go” or TUG test 24, 48 and 72 hours after commencement of study infusion; TUG test is the time in seconds it takes the patient to stand from the chair, walk 3 meters, turn around and sit down again.
- Passive range-of-motion; the range of knee flexion will be recorded by the research nurse using a goniometer at the same follow up time intervals.

Post-operative Analgesia:

- Regular paracetamol (1gram Q6h) and celecoxib (100mg BD) unless contraindications exist.
- Do not prescribe sustained release opioid preparations (OxyContin or M-Eslon)
- Avoid prescribing IV Morphine and Patient Controlled IV Analgesia, unless strong reasons exist (e.g. Chronic pain states or pre-existing therapy).
- Patient will have access to the following PRN analgesia if required.

- Sevredol: Morphine immediate release 10-20mg PO Q2 hours PRN
- Tramadol 50-100mg either PO or IV Q6 hours PRN
- Oxycodone Immediate release (OxyNorm): 5-10mg PO Q2 hours PRN

A trial safety and data adjudication committee with three members independent from the study will be established to adjudicate serious adverse events and determine the need to stop the administration of trial drugs. Given the established safety of the medicine and technique, it is anticipated that this should be infrequent.

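### The exclusion list has no time limit and the moment of randomisation is not fixed, so the protocol permits exclusion after allocation, including for treatment that may be linked to the primary outcome

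*Protocol*

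**What the plan says.** Patients are enrolled "prior to the day of surgery in the preadmission clinic or on the day of surgery at the time of surgical and anaesthetic consent" (2.2 Inclusion Criteria). The catheter is placed at the end of surgery, and no drug goes down it until the infusion is attached in PACU (2.4). On allocation, 2.4 says only: "Randomisation will have taken place using opaque envelopes".

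The exclusion list in 2.2 contains, among others:

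- "Nerve catheter placed outside accepted range (distal to femoral triangle down to the adductor canal"
- "Failure to site adductor canal catheter in the appropriate location"
- "Analgesic technique involving epidural or peripheral nerve blockade (single shot or continuous techniques"
- "If surgical team do not wish to take part or give individually tailored treatment that violate study protocol"

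None of these four carries a time limit. The paragraph below the list leaves management mostly to the treating specialists, suggests a pro forma, and adds that "data surrounding deviation from this pro forma will be collected and included in the final analysis".

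Section 2.5 sets the postoperative opioid rules. One is flat: "Do not prescribe sustained release opioid preparations (OxyContin or M-Eslon". Another asks prescribers to avoid IV morphine and patient-controlled IV analgesia, but makes an exception for strong reasons. The primary outcome is total opioid consumption over 48 hours.

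**The concern.** An exclusion criterion is harmless when it is settled before allocation. Once a patient has been allocated, removal for something that happened later breaks the randomised comparison, and more so if the reason is related to the outcome.

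The list in 2.2 mixes ordinary eligibility facts with events that can arise only at or after catheter placement. The tailored-treatment item is the most sensitive. A breach of the opioid rules in 2.5 happens while the primary outcome is accruing, and extra opioid is itself part of that outcome. If such patients left the trial, the highest opioid users would tend to go, and more of them from the arm with worse analgesia. The observed difference would then be too small. If the rule were used more readily in one arm, the type I error would rise as well.

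**Working it through.** **1. Order of events.** Enrolment takes place in clinic or at consent (2.2). Surgery follows, then catheter placement (2.4), then attachment of the infusion in PACU, by which time randomisation has been done (2.4). The opioid rules and the 48-hour outcome come after that (2.4, 2.5). The order of placement and envelope opening is not given.

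**2. Each criterion against that order.**

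| Item in 2.2 | When it can be judged | Can it fall after allocation? |
|---|---|---|
| Catheter out of range; failed siting | End of surgery | Yes, if envelopes are opened before placement |
| Epidural or peripheral nerve block | Before or after surgery | Yes, no time limit |
| Surgical team declines | Before enrolment or later | Not ruled out |
| Tailored treatment that breaches the protocol | When planned, or when given | Yes, including during the 48 hours |

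**3. Consistency within 2.2.** Management is mostly discretionary and pro forma deviations enter the analysis, yet tailoring that breaches the protocol is a ground for exclusion. The inclusion sentence refers to the pro forma in 2.3 and does not clearly reach the opioid rules in 2.5. It therefore points towards keeping deviators without settling the matter.

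**4. Size.** There is no figure in the plan to reproduce: 1.4 leaves the sample size open and gives only α = 0.05, β = 0.2 and 40 to 60 patients in similar trials. Everything below rests on assumed distributions and assumed drop rules.

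*Normal model.* With 20 or 30 per arm, the effect giving 80% power is d = (1.960 + 0.842)·√(2/n), which is 0.886 SD for n = 20 and 0.723 SD for n = 30. I simulated 40,000 trials with a pooled t-test, dropping every patient above a given centile of the continuous-infusion arm:

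| n per arm | Cut-off | Dropped, continuous / PIB | Mean difference (SD) | Power |
|---|---|---|---|---|
| 30 | none | 0 / 0 | 0.723 | 78.7% |
| 30 | 90th | 10.0% / 2.3% | 0.582 | 66.7% |
| 30 | 80th | 20.0% / 5.9% | 0.498 | 56.2% |
| 20 | none | 0 / 0 | 0.883 | 77.9% |
| 20 | 90th | 10.0% / 1.5% | 0.730 | 66.9% |
| 20 | 80th | 20.1% / 4.2% | 0.631 | 56.6% |

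The difference shrinks by 17% to 31%, for example (0.723 − 0.498)/0.723 = 31%. If only half of the high users are dropped, power is 69% to 73%. For comparison, a 10% loss unrelated to outcome lowers power from 80% to 75.7% by the normal formula.

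With no true effect, the same rule in both arms leaves type I error at 5.0% to 5.2%. Dropping in one arm only gives 8.9% (n = 20) and 11.2% (n = 30) at the 90th centile, and 18.5% and 27.4% at the 80th.

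*Log-normal model.* Assume a continuous-arm median of 60 mg and a PIB/continuous ratio of 0.75. The full mean difference is 0.25·60·exp(s²/2), where s is the log-SD.

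| s | Full difference | After 90th-centile cut | After 80th-centile cut |
|---|---|---|---|
| 0.5 | 17.0 mg | 11.1 mg (−35%) | 8.5 mg (−50%) |
| 0.7 | 19.2 mg | 10.7 mg (−44%) | 7.7 mg (−60%) |

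*Are these cut-offs protocol breaches?* The 90th centile is 60·exp(1.2816·s), or 114 mg at s = 0.5 and 147 mg at s = 0.7. The 80th is 60·exp(0.8416·s), or 91 and 108 mg. The as-needed immediate-release oral morphine in 2.5 is 10 to 20 mg every 2 hours. Over 48 hours that is 24 intervals, so 240 to 480 mg from this item alone. A patient can pass every one of these cut-offs without breaching the opioid rules.

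**The case against.** The case on the other side is substantial.

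- **Siting.** If envelopes are opened after placement, both siting items are ordinary eligibility criteria. If they are opened before, the allocated regimen still cannot cause a siting failure, because no drug enters the catheter before PACU. This stands; what remains is that the protocol does not fix the order.
- **The surgical-team item.** It can be read as covering a team that opts out or plans non-protocol care before enrolment. That reading is fair, but nothing in the text confines the item to it.
- **Removal for poor analgesia.** A reader might infer that patients with uncontrolled pain are to be dropped. No section says so. IV morphine and patient-controlled analgesia are allowed for strong reasons, so their use is not automatically a breach; only sustained-release opioid is flatly barred.
- **Selective exclusion.** A reader might infer that unblinded PACU nurses could steer exclusions. They programme and attach the pump, and nothing gives them a part in deciding who is excluded. The assessing research nurse is blinded. Blinding of the treating clinicians is not stated, so unequal use by arm is not ruled out, but it is not described either.
- **Analysis set.** A statistical analysis plan that is not shown may define it, so its absence from the protocol is no finding. Such a plan could not, however, restore 48-hour data that were never collected because a patient had been excluded.

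**Conclusion.** The concern holds in a limited form. The exclusions have no time limit and the moment of randomisation is not fixed relative to catheter placement. Following 2.2 as written therefore permits exclusion after allocation, and the tailored-treatment ground can be tied to the primary outcome. It also sits badly with the statement that pro forma deviations are analysed. That is short of a proven contradiction, since the two sentences may concern different kinds of deviation.

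The direction follows from the mechanism: a smaller observed difference if high opioid users are removed, and an inflated type I error only if removal differs by arm. The size cannot be derived from the documents. The 17% to 31% (normal) and 35% to 60% (log-normal) reductions assume that every patient above the cut-off is excluded and nobody below it. The as-needed opioid list shows that high use need not be a breach, so these are extreme cases and not expected losses.

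**What to change.** 1. In 2.4, state that the next sealed envelope is opened only after the catheter has been sited and its position accepted. Both siting criteria then act before allocation.
2. In 2.2, limit all exclusions to facts known before randomisation. For the surgical-team item, this means a team that declines, or plans treatment outside the protocol, before the envelope is opened.
3. State that protocol-violating treatment given later is recorded as a deviation, and that the patient stays in follow-up and is analysed in the allocated arm with all opioids counted.

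These are wording changes plus a fixed point for opening the envelope, at almost no cost and with no change to any dose or clinical rule. The small downside is that deviators stay in and may slightly dilute the effect. The changes belong before recruitment, because data not collected on an excluded patient may be lost for good.
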